### **3.3 Study Endpoints**

#### **3.3.1 Pilot Study**

The primary goal of this pilot is to determine the feasibility of recruiting and retaining men into a clinical trial of yoga to improve fatigue and health related quality of life in prostate cancer patients undergoing radiation treatment. The endpoint is the number of evaluable patients accrued, with a minimum target goal of 15 of the first 75 eligible patients approached.

#### **3.3.2 Randomized Phase II Study**

##### **3.3.2.1 Primary Study Endpoints**

The primary goal is to determine the effect size of yoga on fatigue. The endpoint is the difference in BFI fatigue score between time points during radiation therapy and baseline prior to radiation.

### **3.3.2.2 Secondary Endpoints**

The effect size of yoga on ED, UI and general QOL

## **4 Subject Selection and Withdrawal**

### **4.1 Subject Recruitment and Screening**

Patients will be recruited from the Perelman Radiation Oncology Center and will be assessed for eligibility before starting treatment. Patients will be pre-screened for barriers to participation in physical activity using the standard of care metric 'ECOG Performance Status'. All potentially eligible candidates will then be asked to take the Yoga in Prostate Cancer Study Questionnaire (\*\*see appendix\*\*) to assess baseline beliefs, goals and interest in study participation and approached with details of the clinical study to assess their eligibility and interest in enrollment. This survey would be offered to all prostate cancer patients seen in the department of radiation oncology during both the feasibility and randomized phases of the trial. The questionnaires from all patients who complete one will be analyzed as a separate, smaller part of the overall study to better understand barriers and promoters to enrollment. Patients and caregivers will be officially enrolled in the study only after eligibility is confirmed, the informed consent process is performed and relevant signatures are obtained.

## **4.2 Inclusion Criteria**

### Patients

1. Prostate cancer patients undergoing active radiation therapy (external beam radiation with photons and/ or protons). Prior or concurrent androgen deprivation therapy is permitted.
2. Patients of age  $\geq 18$  years, and all races will be included in the study.
3. Patients must have an ECOG Performance Score  $\leq 1$
4. All patients must sign an informed consent form approved for this purpose by the Institutional Review Board (IRB) of the University of Pennsylvania.
5. Patients must be English-speaking.

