### **3 Study Design**

#### **3.1 General Design**

1. This study will have 2 phases, and will consist of a preliminary study of feasibility, and a two-arm, phase 2 randomized study of efficacy, with a go/ no-go decision for phase 2 based on feasibility.
2. Those enrolled in the feasibility study will be part of the yoga treatment arm at analysis time.

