#### **3.2 Study Measures**

1. Baseline information will be collected prior to start of yoga therapy. (age, race/ethnicity, marital/partner status, educational history, income, residence location, travel time to facility, method of travel, details regarding co-morbidities, disease stage, detail of their current radiotherapy).
2. The Brief Fatigue Inventory (BFI) questionnaire is a 9 –item scale that will be used to rapidly assess fatigue severity. The first three questions rate the severity of the patient’s fatigue at its “worst”, “usual” and “now” levels over the last 24 hours, with 0 meaning “no fatigue” and 10 being “fatigue as bad as you can imagine”. Six questions assess the amount that fatigue has interfered with different aspects of the patient’s life during the past 24 hours. The interference items include general activity, mode, walking ability, normal work (includes both work outside the home and housework), relations with others, and enjoyment of life. The interference questions are measured on a 0 -10 scale, with 0 being “does not interfere” and 10 being “completely interferes”. Scores on this scale range from 0-10, with a mean score of 4.7 and S.D of 2.8. The BFI questionnaire will be completed by patients at the following time points:
  - a. Prior to start of radiotherapy i.e. on the day of consultation or on the day of simulation or setup.
  - b. Bi-weekly while receiving radiotherapy

- SD. Scores range from 0 to 25. Scores (>20) indicate normal degree of erectile function. Scores 10> indicate moderate to severe erectile dysfunction. The IIEF will be completed by patients at the following time points:
- a. Prior to start of radiotherapy i.e. on the day of consultation or on the day of simulation or setup.
  - b. In the 4th week of radiotherapy (when treatment-related symptoms are expected to peak)
    - i. A treatment week is defined as 5 consecutive days of radiotherapy. If a patient misses treatment for any reason his treatment week is shifted back one day.
  - c. Within a week of the last yoga class or by the end of radiation.

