### **4.4 Randomization**

Both patients and caregivers will be randomized (without replacement) by lists created using small permuted blocks.

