#### **7.1.2.2 Statistical Methods**

This randomized study is a two-arm longitudinal controlled trial of yoga as a means of reducing fatigue over the course of radiation therapy for prostate cancer, with measures taken prior to treatment, during treatment, and in follow-up. The analysis will include the initial subjects from the feasibility study as an addition to the treatment arm, and we will control for any differences between the feasibility group and the randomized treatment arm using indicators. The primary measure, and most secondary measures, are Likert-style summary scores on a 0-10 scale and will be treated as Gaussian. The exception is retention, which is a binomial count of those remaining enrolled to the end.

Prior to performing analyses, standard data cleaning procedures will be applied (e.g., checking for outliers and data entry errors, creating summary scores for analysis, and checking that analysis assumptions are met). The assumptions underlying the statistical methods will be examined through the use of standard tests of normality, and graphical displays (27). All analyses will be conducted using Stata software (Stata Corporation, College Station, TX).

We will calculate descriptive statistics for all variables in the study. For outcome variables, we will summarize by treatment group (Yoga versus control) and by time point. We will also estimate correlations within subject for each of the study measures taken at different times.

The primary outcome for the randomized, phase II study will be the difference score of BFI fatigue while undergoing radiation therapy minus BFI fatigue prior to radiation. The primary hypothesis will be tested using a two-group t-test to compare difference scores between Yoga and control groups. This will be a one-sided test with type-1 error at  $\alpha=0.05$ . Similar analysis will be conducted using BFI fatigue at follow-up versus pre-radiation, and for all of the FACT-G fatigue measures. We will test the difference using a one-sided z-test. The FACT-G analysis will be repeated for caregivers (Aim 4).

Effect sizes will be reported for all outcome measures as standardized differences. The effect size will reflect the time x treatment interaction, and the standard deviations will be adjusted for within-subject correlation to aid in designing a larger study.

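### Androgen deprivation therapy is permitted but is neither in the listed baseline data nor in the BFI comparison, so an ADT difference between arms would go unadjusted

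*Combined protocol and SAP*

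**What the plan says.** Inclusion criterion 1 in 4.2 states: "Prior or concurrent androgen deprivation therapy is permitted". It sets no limit on timing or duration, and this is the only mention of ADT in the documents. The baseline list in 3.2 (item 1) is itemised; its disease and treatment entries are "details regarding co-morbidities, disease stage, detail of their current radiotherapy". In 4.4, subjects are "randomized (without replacement) by lists created using small permuted blocks", with no stratification factor named.

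In 7.1.2.2, "The primary hypothesis will be tested using a two-group t-test to compare difference scores between Yoga and control groups". The score is BFI during radiotherapy minus BFI before it. Under 3.2 the baseline BFI may be taken "on the day of consultation or on the day of simulation or setup".

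On the pilot patients, 3.1 says: "Those enrolled in the feasibility study will be part of the yoga treatment arm at analysis time". The only adjustment mentioned is in 7.1.2.2: "we will control for any differences between the feasibility group and the randomized treatment arm using indicators". The t-test as written has no such term. Erectile dysfunction is a secondary endpoint (3.3.2.2), measured by the IIEF.

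**The concern.** ADT is a background cancer treatment that some men will have and others will not. If it affects fatigue or erectile function, a difference in ADT use between arms becomes part of the estimated yoga effect. That link is a clinical premise: the background section discusses fatigue and erectile dysfunction in relation to cancer and radiotherapy and does not mention ADT.

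There are two routes. Among the randomised men, about 20 per arm after dropout, ADT use can differ by chance. The 15 feasibility men were never randomised, so nothing in the design makes their ADT use match that of the controls.

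Section 7.1.2.1 gives the trial's purpose as estimating effect sizes for a larger study. An estimate that cannot be described or adjusted for ADT from the data the plan lists is less useful for that.

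**Working it through.** **Inputs from the documents.** Patients 35 v 20, made up of 20 v 20 randomised plus 15 feasibility men in the yoga arm; target effect d = 0.7; one-sided alpha 0.05; power 80%; SD of the difference score similar to that of the raw score (all 7.1.2.1). BFI SD 2.8 (3.2).

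**Assumptions, not in the documents.** ADT prevalence 30% to 50%. ADT effect on the BFI change score of 0.25, 0.5 or 0.8 SD.

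**1. The plan's own figures.** In SD units, SE = √(1/35 + 1/20) = 0.280. Power = Φ(0.7/0.280 − 1.645) = 80.3%. The 95% interval width is 2 × 1.96 × 0.280 = 1.10 SD. Both agree with 7.1.2.1.

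**2. Chance of an ADT gap.** ADT counts are taken as two independent binomials with common prevalence p. The entries are the probability that the arms differ by 20 percentage points or more, in either direction.

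| p | 35 v 20 (as planned) | 20 v 20 (randomised only) |
|---|---|---|
| 30% | 13% | 23% |
| 40% | 15% | 26% |
| 50% | 16% | 27% |

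The 35 v 20 column assumes that feasibility and randomised men have the same prevalence. The 20 v 20 column applies if the feasibility indicator is fitted, because the treatment contrast then rests on the randomised men.

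**3. Effect of a 20-point gap on the 35 v 20 estimate.** Shift = 0.20 × ADT effect. BFI points = shift × 2.8. Conditional type I error (gap favouring yoga) = 1 − Φ(1.645 − shift/0.280). Conditional power (gap against yoga) = Φ((0.7 − shift)/0.280 − 1.645).

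| ADT effect (SD) | Shift (SD) | BFI points | Type I error, gap favours yoga | Power at d = 0.7, gap against yoga |
|---|---|---|---|---|
| 0.25 | 0.05 | 0.14 | 7.1% | 75% |
| 0.5 | 0.10 | 0.28 | 9.9% | 69% |
| 0.8 | 0.16 | 0.45 | 14.1% | 61% |

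The last two columns are conditional on a gap of that size having occurred.

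**4. The non-randomised men.** If 20% of the feasibility men and 40% of the randomised men used ADT (assumption), the pooled yoga arm would have (15 × 0.20 + 20 × 0.40)/35 = 31%, against 40% in control. That is an expected gap of about 9 points, which randomisation does not remove.

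**5. Gain from adjustment.** With 50% on ADT, residual SD = √(1 − 0.25 × effect²) = 0.99, 0.97 or 0.92 for the three effects. Power at 35 v 20 becomes Φ(0.7/(residual SD × 0.280) − 1.645) = 80.8%, 82.5% or 86.0%, against 80.3% unadjusted (normal approximation, before the feasibility indicator is added).

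With the indicator, SE = √(1/20 + 1/20) = 0.316 and power is 71.5% without ADT. With ADT added, the same formula with 0.316 gives 72.1%, 73.9% or 77.9%. The drop from 80.3% to 71.5% comes from the indicator that the plan already announces, not from ADT.

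**The case against.** The strongest reply is that the endpoint is a change score in a trial that randomises most of its patients.

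- **Change score.** A stable ADT effect already present at baseline cancels. This stands, and long-established or completed ADT may add little to BFI change. What is left is ADT whose effect changes between baseline and the on-treatment measures. The documents do not say how common that is, so the low end of the effect range may be nearer the truth.
- **Chance imbalance.** Among randomised men it is already covered by the confidence interval and does not raise the unconditional type I error. This stands too. A reader might take the conditional error rates in the working as evidence that the test is invalid; they are not. The argument for adjusting is precision and protection once a gap has occurred. The systematic route is the feasibility group alone.
- **Size.** A 20-point gap has about a one-in-seven chance at 35 v 20, in either direction, and moves the estimate by well under one standard error. This stands.
- **Charts.** A reader might infer that the team could never detect an ADT imbalance. The documents do not support that: this is one centre, and 9.2 counts hospital records and clinical charts among source documents. ADT is unspecified, not unobtainable.
- **Stratification and baseline timing.** A reader might also conclude that the list must be stratified by ADT, or that every baseline BFI should move to simulation or setup. Unstratified blocks are a legitimate choice for about 40 men. The documents do not say when ADT starts, so no benefit from moving the baseline can be shown.

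The reply does not explain why a permitted systemic treatment is missing from an otherwise itemised baseline list, or why the comparison has no term for it when part of one arm was not randomised.

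**Conclusion.** The omission is certain from the text: ADT is permitted in 4.2 and appears neither in the baseline data of 3.2 nor in any analysis in 7.1.2.2. The consequence is moderate and conditional. It depends on ADT affecting fatigue or erectile function, on that effect changing after baseline, and on prevalence, none of which the documents give. Under the ranges shown, the likely distortion of the BFI estimate is 0.05 to 0.16 SD for a 20-point gap. This is small beside the 0.28 SD standard error, but not trivial for a study meant to supply an effect size of the order of 0.7 SD.

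A reader might go further and say that an ADT effect will be read as a yoga effect. The documents show only that it could be, and that the plan as written takes no step to prevent it. The change is worth making because it costs little and gives some precision back.

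**What to change.** - **3.2, baseline data:** add ADT status (none, prior, current or planned during radiotherapy) and ADT start date.
- **7.1.2.2, analysis:** replace the unadjusted t-test on BFI change, and the corresponding IIEF comparison, with a linear model containing treatment, the feasibility-group indicator already announced, and ADT. Report ADT status by arm, with feasibility men shown separately from randomised yoga men.
- **4.4, randomisation:** stratifying the list by ADT is optional. It would not balance the feasibility men.

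Cost: one chart-derived entry (status with start date) per man and one degree of freedom, if ADT enters the model as current or planned versus not; using all three levels takes two. No change in sample size, visits or baseline timing is needed. If randomisation has already begun, recording from charts and adjusting are still possible, and the model should then be fixed before outcomes are compared by arm.

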### Caregivers

1. Subject is age  $\geq 18$  years
2. Subject is English-speaking
3. Subject must sign an informed consent form approved for this purpose by the Institutional Review Board (IRB) of the University of Pennsylvania.

### **4.3 Exclusion Criteria**

#### Patients

1. Patients with medical restrictions that may interfere with or prevent them from taking part in the yoga interventions per their physician orders as evaluated by ECOG Performance Status score.
2. Active, regular cigarette smokers, such that smoking may interfere with relaxation and breathing modalities of the yoga interventions. (Smokers that have been smoke-free for 6 months may be included)
3. Patients who currently practice or have recently practiced yoga (taken a yoga class on a regular basis in the last 6 months).
4. Patients who are undergoing chemotherapy for any reason
5. Patients with evidence of metastatic disease

#### Caregivers

1. Subjects that are unwilling or unable to provide informed consent
2. Subjects with medical restrictions that may interfere with or prevent them from taking part in the yoga interventions
3. Active, regular cigarette smokers, such that smoking may interfere with relaxation and breathing modalities of the yoga interventions. (Smokers that have been smoke-free for 6 months may be included)
4. Patients who currently practice or have recently practiced yoga (taken a yoga class on a regular basis in the last 6 months).

### **4.4 Randomization**

Both patients and caregivers will be randomized (without replacement) by lists created using small permuted blocks.

## **4.5 Early Withdrawal of Subjects**

### **4.5.1 When and How to Withdraw Subjects**

The principal investigator may withdraw subjects if it is felt to be necessary for the health and safety of the subject. Additionally subjects may be withdrawn for not following study instructions. We expect up to 20% of subjects to drop out from the study due to time constraints, use of other CAM, and concurrent illness.

### **4.5.2 Data Collection and Follow-up for Withdrawn Subjects**

All efforts will be made to connect with the subjects by mail and/or phone to better understand the reasons for the withdrawal and make an assessment for better future recruitment, as well as for a better implementation of the yoga interventions.

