## **6 Study Procedures**

### Feasibility and Yoga Treatment Arm

Subjects will participate in two 75 minute sessions per week for the duration of radiation treatment with a yoga instructor offered for free by Patient Family Services in the Perelman Center of Advanced Medicine. Numerous sessions will be offered each week. Each session will begin with breathing and centering techniques (taking inventory of the levels of energy, posture, stress level, emotions, and breath). Yoga poses will consist of the following and can be modified based on patient needs: Sitting on chair: neck and shoulder series (neck and shoulders side, front and back movements, shoulder rolls, and arms movement), Table pose with opposite arm and leg movement. Side bent. Simple chair twist. Standing poses: Mountain pose, Warrior II series, Half Moon variation at the wall, Front warrior series, forward stretch/ bend variation with a chair. Recline poses will include: inverted lake pose (legs up the wall with a blanket for support), bridge pose variation, recline/ sided bound angle pose, modified Camel pose at the wall, modified Shoulder stand (legs up the wall with block support), reclining big toe posture with a belt, and corpse pose (Savasana – final rest). Modifications can and will be made based on

each subjects specific needs and physical restrictions. Poses will be added progressively. Not all poses will be done each session. Additionally subjects will fill out 4 types of QOL forms at various points during the study. The first is to be completed prior to start of radiation treatment, bi-weekly during treatment and within a week of the last yoga class or by the end of radiation

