### No Yoga Treatment Arm

Control patients who are randomized to standard of care will not undergo any yoga intervention or participate in any structured yoga program during the study duration. They will undergo cancer and side effect treatment per standard of care, and they will be asked to complete all study-related questionnaires at the same time points as the patients in the yoga treatment arm.

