### 7.1.2.3 Subject Population(s) for Analysis

Statistically evaluable subjects are those who have attended at least 50% of the available yoga sessions offered on the days they receive radiation treatment.

	Subject attends treatment	Subject misses treatment (inclement weather or machine downtime)
Yoga offered	Counts towards evaluability	Counts towards evaluability
Yoga session not offered	Doesn't count for or against evaluability	Doesn't count for or against evaluability

- All caregivers will follow the same evaluability guidelines as the radiation therapy population. If their associated subject undergoes treatment, the caregiver is also considered to have undergone “treatment”.

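### No outcome collection is specified after withdrawal, and one ground for withdrawal bears mainly on the yoga arm, so loss of BFI data can differ by arm

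*Combined protocol and SAP*

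**What the plan says.** On withdrawal, section 4.5.1 gives the investigator discretion on health and safety grounds and adds: "Additionally subjects may be withdrawn for not following study instructions". It goes on: "We expect up to 20% of subjects to drop out from the study due to time constraints, use of other CAM, and concurrent illness".

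Section 4.5.2, whose title announces data collection for withdrawn subjects, commits the team to this: "All efforts will be made to connect with the subjects by mail and/or phone to better understand the reasons for the withdrawal". The stated use is better recruitment and better delivery of yoga in future. No outcome form is mentioned.

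The instructions differ by arm. In section 6, for yoga: "Subjects will participate in two 75 minute sessions per week for the duration of radiation treatment". Control men "will not undergo any yoga intervention or participate in any structured yoga program during the study duration" and complete the same questionnaires at the same times.

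The primary outcome in section 7.1.2.2 is the "difference score of BFI fatigue while undergoing radiation therapy minus BFI fatigue prior to radiation", compared by a one-sided two-group t-test. Section 7.1.2.3 defines the analysis population: "Statistically evaluable subjects are those who have attended at least 50% of the available yoga sessions offered on the days they receive radiation treatment". It gives no corresponding rule for control patients. Section 7.1.2.1 recruits 48 so as to end with 40.

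**The concern.** A man assigned to yoga can be withdrawn for not attending classes. A control man has no classes to miss, although he could be withdrawn for breaking another instruction. Once a man is withdrawn, the plan seeks his reason and nothing else, so BFI forms that fall due later are not collected. Yet a man withdrawn for missing classes would normally still be attending for radiotherapy and could be asked.

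The outcome is fatigue and the intervention takes effort, so tired men may plausibly miss more classes. If so, the yoga men left with data would be the less fatigued ones, and the comparison would lean towards yoga, which is also the direction of the one-sided test. The stated goal of phase II is to estimate effect sizes for a larger study, so such a bias would pass into that study's design. An analysis set can be redefined later, but forms that were never collected cannot be recovered.

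**Working it through.** **The plan's own figures.** Inputs from section 7.1.2.1: 35 yoga v 20 control, d = 0.7, one-sided alpha 0.05. The SD of the difference score is taken as about equal to the raw SD.

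- Standard error in SD units: sqrt(1/35 + 1/20) = 0.280.
- Power: 0.7/0.280 − 1.645 gives 80.3% by the normal approximation and 79.4% by the t distribution. The stated 80% is reproduced.
- 95% CI width: 2 × 1.96 × 0.280 = 1.10 SD, as stated.

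The power calculation is not at fault. What matters here is how it treats dropouts: 40 × 1.2 = 48 recruited to give 40. Men who drop out are counted as absent from the analysis.

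**Is post-withdrawal collection provided elsewhere?**

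- Section 3.2 ties BFI to radiotherapy (before it, then bi-weekly during it). It says nothing about withdrawn men.
- Section 9.1 seeks at least vital status, and only from men who revoke authorization to use their health information.
- Section 7.1.2.2 gives no missing-data method and no sensitivity analysis.

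The answer is no.

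**Size of the possible bias.** If a fraction q of the yoga arm is lost and those men would have had a BFI change s SD worse than the men retained, the retained mean is too favourable by q × s.

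Inputs from the documents: 48 phase II men, taken as 24 per arm because the plan's 20 v 20 implies equal allocation; 15 pilot men added to yoga (24 + 15 = 39; 48 + 15 = 63); loss up to 20%; BFI SD 2.8 (section 3.2); detectable effect 0.7.

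Assumptions: s = 0.5 to 1; no usable BFI from lost men; control loss unrelated to fatigue; the 15 pilot men all retained, because the plan counts them as already evaluable.

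- Men lost: 0.20 × 24 = 4.8. Fraction of the yoga arm: 4.8/39 = 12.3%.
- Bias: 0.123 × 0.5 = 0.06 SD to 0.123 × 1 = 0.12 SD.
- In BFI points: × 2.8 = 0.17 to 0.34.
- Relative to the detectable effect: ÷ 0.7 = 9% to 18%.

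If instead 20% of all yoga men are lost: 0.20 × 0.5 to 0.20 × 1 = 0.10 to 0.20 SD, or 0.28 to 0.56 points, or 14% to 29% of 0.7.

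**Effect on the test.** A simulation under no yoga effect used 40,000 trials per scenario, with 39 yoga v 24 control before loss. Loss occurred in the yoga arm only, and the propensity to be lost had correlation 0.3 to 0.7 with the BFI change. The nominal one-sided error is 5%.

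| Yoga-arm loss | Bias (SD) | One-sided type I error |
|---|---|---|
| 10% | 0.06 to 0.14 | 7.9% to 13.3% |
| 20% | 0.11 to 0.25 | 10.6% to 24.6% |

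The loss shares and correlations are assumptions, and having no control loss is the unfavourable case.

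**The case against.** A reader might infer that the plan treats stopping yoga and leaving the study as one event, so that every man who stops yoga drops out of the primary comparison. The documents do not say that. Withdrawal for not following instructions is discretionary. A man who attends half the sessions remains evaluable, and section 7.1.2.3 goes on to grade attenders in bands starting at 50%. The BFI schedule follows radiotherapy, not class attendance, and nothing tells staff to stop the forms when a man stops yoga. Scores taken before withdrawal also exist and might already yield a difference score, although the plan does not say whether they count. All of this stands and narrows the point to forms due after a formal withdrawal.

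It is also tempting to treat the link with fatigue as established. Section 4.5.1 names time constraints, other complementary therapies and concurrent illness. Fatigue is not listed, and the last two could remove control men as well. The direction of the bias is therefore an inference.

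The 20% is an upper figure for all causes in both arms. Applying it to all 39 yoga men sits badly with the plan's own count, which takes the 15 pilot men as already evaluable. The smaller range is the better illustration. Even 0.20 SD lies well within the CI half-width of about 0.55 SD.

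Finally, men withdrawn for missing classes would mostly fall below 50% attendance and be non-evaluable anyway, so collecting their forms alone would not change the planned comparison. That is correct, and the remedy must cover the analysis population too. None of these objections supplies the missing provision for outcome data after withdrawal.

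**Conclusion.** The gap is real and should be fixed. As written, the plan allows withdrawal on a ground that includes class attendance in one arm only, and it collects no BFI afterwards. Together with the handling of dropouts in the sample size and the attendance rule, this lets outcome loss differ by arm. It would favour yoga if the more fatigued yoga men are the ones lost.

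The illustrative size is 0.06 to 0.12 SD, rising to 0.10 to 0.20 SD if a fifth of all yoga men are lost. Both ranges rest on the assumed shortfall of 0.5 to 1 SD, on no usable BFI from lost men and on control loss unrelated to fatigue. The documents do not show that the loss will be this large, or that it will be driven by fatigue. For a phase II trial with a CI about 1.1 SD wide, this is a matter to correct, not one that invalidates the design.

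**What to change.** Three changes belong together:

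- **Section 4.5:** state that missing or stopping yoga does not by itself end outcome collection.
- **Section 4.5.2:** use the mail or phone contact already planned, or the radiotherapy visit, to collect the remaining scheduled BFI, FACT-G, IIEF and IPSS forms as well as the reason, unless the man withdraws consent for data.
- **Section 7.1.2.3:** include all randomised men with available BFI in the randomised comparison, whatever their attendance, and keep the attendance-based set as supportive.

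No change is proposed to when yoga itself is stopped.

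The cost is a few sentences and a few extra forms at contacts that mostly exist already. Some men will decline, so the loss is reduced but not removed. The estimated effect may be diluted by non-attenders. Against that, if BFI were obtained from all 63 enrolled (39 v 24), power at d = 0.7 would be 84.7% by the t distribution, compared with 79.4% at 35 v 20, before any dilution.
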